9.3. Variables

9.3.1. Outcomes

The primary outcome is MCM. The secondary outcomes are SA, induced termination, stillbirth, livebirth, SGA, preterm birth, postnatal growth deficiency and

infant developmental. The study outcomes will be identified by ICD-10 diagnosis and procedure codes, CPT^{®2} procedure codes, and HCPCS procedure codes on claims. All outcomes will initially be identified via claims-based algorithms. Potential cases of MCM, induced termination, SGA, preterm birth, postnatal growth deficiency and infant developmental delay, and a sample of livebirths identified via claims-based algorithms will be adjudicated via medical records.

9.3.1.1. Pregnancy outcomes

The pregnancy outcomes to be assessed are:

- SA defined as the loss of pregnancy before the 20th week of gestation
- Induced termination defined as an intervention to end a pregnancy so that it does not result in a livebirth
- Stillbirth defined as the loss of pregnancy at or after the 20th week of gestation
- Livebirth a delivered fetus with any sign of life (eg, voluntary movement, heartbeat) regardless of gestational weeks

Lists of ICD-10 diagnostic codes are provided in ANNEX 2. ADDITIONAL INFORMATION.

9.3.1.2. Infant outcomes

The infant outcomes to be assessed are:

MCM – defined as a structural abnormality with surgical, medical, or cosmetic importance and will exclude chromosomal abnormalities or physiological features due to complications of prematurity, such as cryptorchidism, inguinal hernia, or isolated patent ductus arteriosus in infants born less than 37 weeks of gestation. There are 3 main types of congenital malformations – deformation, disruption, and dysplasia. A deformation occurs when an intrinsically normal structure is prevented from normal intrauterine growth by an external constraint. In a disruption, a normally forming tissue or organ is destroyed by an abnormality of the intrauterine environment. Dysplasia is a morphologic anomaly arising either prenatally or postnatally from dynamic or ongoing alteration of cellular constitution, tissue organization or function within a specific organ or a specific tissue type (Hennekam et al. 2013). Classifications will be based on guidelines from the New York State Department of Health Congenital Malformations Registry and the European Surveillance of Congenital Malformations (EUROCAT 2020). All identified MCMs will be counted, overall, and classified by body system. If numbers allow, patterns of specific congenital malformations will be described.

² CPT copyright 2022 American Medical Association. All rights reserved.

- SGA defined as birthweight below the 10th percentile for gestational age
- Preterm birth defined as a live birth at or before the 37th week of gestation
- Postnatal growth deficiency
- Infant developmental delay

Lists of ICD-10 diagnostic codes are provided in ANNEX 2. ADDITIONAL INFORMATION.

9.3.1.3. Medical record confirmation of outcomes

Pregnancy and infant outcomes will be assessed using claims-based algorithms from the literature with adequate PPVs when available, otherwise confirmed via medical records. Andrade et al. observed a PPV of 83% for their ICD-10-based stillbirth algorithm, developed within an electronic health record database (Andrade et al. 2021). A recent Optum publication observed a PPV of 84.7% for the identification of SA (Chomistek et al. 2022). Optum proposes to use these published algorithms to identify SA and stillbirth.

Given that most pregnancies are expected to end in a livebirth, a random sample of 200 livebirths will be selected for medical record confirmation and validation of the livebirth identification algorithm, which relies on the presence of outcome-related ICD-10 codes. This conservative sample size is sufficient to exclude from the 95% confidence interval (CI) a PPV <80% if the true PPV is 85% (Schaeffer et al. 1990). Livebirths are identified via ICD-10 codes shown in ANNEX 2. ADDITIONAL INFORMATION.

Using medical records to confirm pregnancy and infant outcomes allows for a highly sensitive and specific outcome definition because medical records may be sought for all potential outcomes (high sensitivity) and each potential outcome is adjudicated (high specificity). The literature will be re-assessed following delivery of the final accrual report to identify alternative stillbirth and/or SA algorithms and algorithms for the remaining outcomes. If suitable algorithms are found, the proposed approach may be modified to use algorithms for additional outcomes (Tonelli et al. 2016).

For outcomes for which medical record confirmation is deemed necessary, a detailed review of the chronological listing of relevant claims (ie, claims profile) will be reviewed for each of the potential cases in order to:

- Determine if the claims listing for each potential case contains sufficient information to be included in the medical record procurement process; and
- Determine the medical site of treatment most likely to yield medical records with the necessary information to confirm case status.

Optum, with input from a clinician, will develop a medical record review form that will include clinical elements necessary to confirm the outcome diagnosis. Providers will be asked to send all available medical information occurring during the period of interest

(surrounding the service date of the relevant claim). This information will include, but is not limited to:

- Labor and delivery records
- Office visit notes
- History and physical exam reports
- Laboratory reports
- Diagnostic imaging reports
- Hospital discharge summaries
- Surgical reports
- Histology/pathology reports
- Consultation/specialist notes

For each potential case, medical records will be sought if the patient is eligible for medical record retrieval. Approximately 50% of patients in the ORD are eligible for medical record retrieval. Patients who are ineligible for medial record retrieval include those from health plans that contract for administrative services only; access to medical records is not allowed for patients enrolled in these plans. For each eligible case, 1 medical record will be requested from 1 provider. Of those that are requested, approximately 70% to 85% of the medical records are expected to be successfully obtained (Johannes et al. 2007, Seeger et al. 2006). Therefore, the overall proportion of the ORD available for medical record validation is approximately 35 to 42.5%. Optum will seek up to 550 medical records.

Two clinical consultants with expertise in the field of teratology will be identified for the adjudication of MCMs, and 2 clinical consultants in the field of obstetrics will be identified for the adjudication of all other outcomes. Each pair of clinicians (blinded to study drug exposure) will review the clinical data for each potential case and adjudicate the outcomes. Each record will be adjudicated by 2 clinicians independent of one another, and consensus will be sought for discrepancies in adjudication results between the clinicians. Optum will work with the clinicians to arrive at consensus adjudications, and the Optum epidemiologist on the project will arbitrate the process. Optum will work with outside vendors as needed to procure the medical records and conduct the outcome adjudication.

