9.5. Study size

The planned sample size incorporates several assumptions derived from published literature, including the following approximate prevalence of pregnancy outcomes:

- Under 1% of pregnancies result in stillbirth (FDA 2002)
- 14% of pregnancies result in SA or miscarriage (FDA 2002)
- 18% of pregnancies have historically been expected to end in induced termination (Jones et al. 2017)
- 3% of live born infants have a major birth defect in the US each year (March of Dimes 2015)
- 10% of live born infants are born preterm or SGA (CDC 2008, Ferré et al. 2016)

Based on these reference percentages, the following assumptions were made for sample size calculation:

- $\alpha = 0.05$
- Power=0.8
- 1:2 matching
- Outcome prevalence as cited above

Table 1 and Table 2 show the minimum required number of PAXLOVID-exposed pregnancies required to proceed to the secondary objective of comparative analyses. Comparative analyses will be conducted if the sample size to detect a RR > 2.0 is achieved for each outcome; target sample size may be achieved for some outcomes but not others.

To detect a RR > 2.0 at 80% power a minimum of 127 PAXLOVID-exposed pregnancies are required for SA, 251 for SGA and preterm birth, and 2,212 for stillbirth, the rarest of the outcomes (Table 1). A minimum of 938 PAXLOVID-exposed pregnancies during the first trimester are required for the primary outcome of MCM (Table 2).

Fewer PAXLOVID-exposed pregnancies are required to detect an RR of > 2.5 at 80% power: 63 for SA, 127 for SGA and preterm birth, and 1,142 for stillbirth. For MCM, the minimum number of pregnancies with PAXLOVID exposure during the first trimester is 482. These estimates are based on 1:2 matching; however, the analyses for this study will utilize IPTW for confounding adjustment. Sample size calculations are based on 1:2 matching as a conservative estimate due to the retention of all eligible pregnancies in IPTW. Power for the analysis of induced termination will be similar to that for SA. The majority of pregnancies end in livebirth; therefore, power is expected to be adequate for this outcome.

Table 1. Sample Size Required for 80% Power to Detect Relative Risks (As or More Extreme) for Pregnancy Outcomes, with 1:2 Matching

Outcome	Prevalence of Outcome	RR	PAXLOVID-Exposed Pregnancies with Observed Outcomes Needed*	PAXLOVID-Exposed Pregnancies Needed**
SA	14%	2	101	127
		2.5	50	63
Stillbirth	1%	2	1,769	2,212
		2.5	913	1,142

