^{*} Sample size calculated using PROC POWER function in SAS with a two-sided likelihood ratio chi-square test, and the specified relative risk and prevalence in the unexposed (SAS EG V8.2, SAS Institute Inc., Cary, NC).

Table 2. Sample Size Required for 80% Power to Detect Relative Risks (As or More Extreme) for Infant Outcomes, with 1:2 Matching

Outcome	Prevalence of Outcome	RR	PAXLOVID- Exposed Livebirths Needed*	PAXLOVID- Exposed Pregnancies Needed**
MCM	3%	2	572	938
		2.5	294	482
Preterm birth	10%	2	153	251
		2.5	77	127
SGA	10%	2	153	251
		2.5	77	127

^{**} A divisor of 0.80, which is the proportion of ongoing pregnancies for which an outcome is eventually observed in DAPI, was used to calculate the number of exposed pregnancies needed.

Table 2. Sample Size Required for 80% Power to Detect Relative Risks (As or More Extreme) for Infant Outcomes, with 1:2 Matching

Outcome	Prevalence of	RR	PAXLOVID-	PAXLOVID-
	Outcome		Exposed	Exposed
			Livebirths	Pregnancies
			Needed*	Needed**

^{*} Sample size calculated using PROC POWER function in SAS with a two-sided likelihood ratio chi-square test and the specified relative risk and prevalence in the unexposed (SAS EG V8.2, SAS Institute Inc., Cary, NC).

Following initial accrual results from the first interim report, it was observed that fewer Cohort 2 pregnancies were accrued than PAXLOVID-exposed pregnancies, at a ratio of approximately 5:1, suggesting that matching of 2 comparators to each PAXLOVID pregnancy is unlikely to be feasible. Assuming a final ratio of 5 PAXLOVID-exposed pregnancies to each Cohort 2 pregnancy, a minimum sample size of 3,352 PAXLOVID-exposed pregnancies (and 670 Cohort 2 pregnancies) will be required to be accrued during the first trimester exposure window to detect a RR \geq 2.0 at 80% power for MCM. To detect a RR \geq 2.5, 1,664 PAXLOVID-exposed pregnancies (and 333 Cohort 2 pregnancies) will be required.

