9.7.2.3. Comparative safety analyses

The comparative analysis will estimate prevalence ratios and corresponding 95% CIs for each of the pregnancy or infant events comparing the PAXLOVID exposed pregnancy cohorts to the comparator pregnancy cohorts in the same exposure window (eg, Cohort 1 first trimester cohort versus Cohort 2 first trimester cohort; Cohort 1 first trimester cohort versus Cohort 3 first trimester cohort). Prevalence will be estimated for these outcomes because they develop during gestation but are only observable at birth; thus, only the prevalence at birth

can be calculated. Crude (unadjusted) and IPTW-adjusted prevalence ratios will be reported along with corresponding 95% CIs. The prevalence ratios will be estimated using robust Poisson regression models (Chen et al. 2018), with analysis of log-binomial models as sensitivity analysis.

Analyses based on claims-identified cases will be presented. However, the primary comparative analyses in the final report will only include outcomes that have been confirmed via medical record review or identified via published validated algorithms.

Planned analyses for each outcome are described in Table 4.

Comparative analyses will be performed overall and among subgroups according to presence of COVID-19 diagnoses occurring prior to exposure to cohort medications, as well as by hospitalization status at the time of COVID-19 diagnosis, sample size permitting.

Analyses will be conducted on MCMs collectively as a whole, with subgroup analyses by MCM subtype (for example, organ system affected) performed as sample size allows. The number of pregnancies with each outcome will serve to guide the analyses that are feasible.

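### SA and stillbirth enter the primary comparison unconfirmed, from algorithms with cited PPVs of 84.7% and 83%, and no planned analysis or sample size allows for outcome misclassification

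*Protocol*

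**What the plan says.** Section 9.3.1.3 adopts published algorithms for SA and stillbirth. For SA, "A recent Optum publication observed a PPV of 84.7% for the identification of SA". For stillbirth, the cited validation study, done in an electronic health record database, "observed a PPV of 83% for their ICD-10-based stillbirth algorithm". Section 9.3.1 lists the outcomes to be adjudicated from medical records, and neither SA nor stillbirth is on that list.

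Section 9.7.2.3 restricts the primary comparative analysis to outcomes "confirmed via medical record review or identified via published validated algorithms", so algorithm cases have the same standing as confirmed ones. Section 9.7.2.2 uses the number of cases as the numerator for prevalence.

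Sections 9.7.3 and 9.7.4 plan work on exposure timing, unmeasured confounding, unobserved outcomes and non-linkage, missing or uninformative records, individual comparators, any PAXLOVID exposure, log-binomial models and subgroups. None of these covers false-positive or missed SA and stillbirth.

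In section 9.5, "To detect a RR > 2.0 at 80% power a minimum of 127 PAXLOVID-exposed pregnancies are required for SA", and 2,212 for stillbirth. These sizes decide whether a comparison is made: "Comparative analyses will be conducted if the sample size to detect a RR > 2.0 is achieved for each outcome".

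**The concern.** A PPV of 83% to 85% means that about 15% to 17% of counted cases are expected to be false. If those false cases are unrelated to the drug, they dilute a real difference between cohorts and pull the prevalence ratio toward 1. More accrual does not cure this. It only narrows the interval around the diluted value.

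This is a safety study, so an SA or stillbirth ratio near 1 is likely to be read as reassuring. A reader would need to know how much of that could come from outcome error, and the plan provides no analysis that says so. Table 1 also acts as the entry condition for the comparison while treating every counted case as true and every true case as counted.

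**Working it through.** **Inputs.** From section 9.5: alpha 0.05, 1:2 allocation, a "two-sided likelihood ratio chi-square test", comparator risks of 14% (SA) and 1% (stillbirth), RR 2.0, Table 1 sizes of 101 and 1,769 exposed pregnancies with observed outcomes, and the divisor 0.80. From section 9.3.1.3: PPV 0.847 and 0.83. Assumed, because the protocol does not give it: sensitivity Se.

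**Power formula.** λ = 2 Σ n_g [p_g ln(p_g/p̄) + (1−p_g) ln((1−p_g)/(1−p̄))], where p̄ is the pooled risk. Power = P(χ²₁(λ) > 3.841).

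**Step 1: reproduce Table 1.** The sizes 101 and 1,769 come out exactly only when the single share n carries the baseline risk and the double share 2n the raised risk. In the layout as described (n exposed at 2p₀, 2n comparators at p₀) the formula needs 96 and 1,643. In that described layout the stated sizes have:
- SA: λ = 8.318, power 82.2%
- Stillbirth: λ = 8.454, power 82.8%

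The reversed layout is a separate matter that the sponsor should check. The steps below use the layout as described.

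**Step 2: add outcome error with Se and the false-positive rate (FPR) equal in both cohorts.** Apply the cited PPV in the comparator cohort, with 14% and 1% as true risks:
- FPR = Se × p₀ × (1−PPV)/PPV ÷ (1−p₀)
- Observed risk = Se × p + (1−p) × FPR
- Dividing the two observed risks, Se cancels: observed RR = PPV × RR + (1−PPV) × (1−RR·p₀)/(1−p₀)

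SA: 0.847 × 2 + 0.153 × 0.72/0.86 = 1.694 + 0.128 = **1.82**

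Stillbirth: 0.83 × 2 + 0.17 × 0.98/0.99 = 1.660 + 0.168 = **1.83**

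At Se = 1 the observed risks are 30.1% v 16.5% (SA) and 2.20% v 1.20% (stillbirth).

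**Step 3: power at the Table 1 sizes under that model.**

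| Se | SA power (n = 101) | SA pregnancies needed (stated 127) | Stillbirth power (n = 1,769) | Stillbirth pregnancies needed (stated 2,212) |
|---|---|---|---|---|
| 1.00 | 76.5% | 111/0.80 = 139 | 77.4% | 1,888/0.80 = 2,360 |
| 0.80 | 64.6% | 146/0.80 = 183 | 67.8% | 2,367/0.80 = 2,959 |

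**Step 4: the other error model, equal PPV in both cohorts.** Observed risk = Se × p/PPV in each cohort, so the ratio stays at 2.0. Power is about 89% for both outcomes at Se = 1, and 82% to 83% when Se equals the PPV. It falls to 73% (SA) and 76% (stillbirth) at Se = 0.70.

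**Step 5: absolute risks.** Observed/true in the comparator cohort = Se/PPV. For Se from 0.80 to 1.00 this is 0.94 to 1.18 (SA) and 0.96 to 1.20 (stillbirth), a range that spans 1.

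**The case against.** The strongest reply is that a PPV fixes neither sensitivity nor the false-positive rate in each cohort. A reader might infer that Table 1 falls below 80% power on the protocol's own figures. It does not: the shortfall needs the added assumption of a common false-positive rate, and Step 4 removes it whenever the PPV is equal in both cohorts and sensitivity is at least about the PPV. This stands.

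A reader might also infer that the error is bound to hide harm. That is not established. Annex 2 lists O31.2 and O36.4 under both SA and stillbirth, so some errors may be swaps between the two kinds of loss, which could rise with a drug effect on loss. Against this, at a true RR of 2.0 an equal PPV requires the false-positive rate among exposed non-cases to be about 2.4 times (SA) or 2.0 times (stillbirth) that among comparators. Since nothing in the protocol has the algorithms use drug exposure, a common rate is a reasonable default, but it remains an assumption.

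Two further readings fail. If 14% and 1% were algorithm-observed risks, power would be 68% to 69%. But section 9.5 takes them from published literature ("14% of pregnancies result in SA or miscarriage"; "Under 1% of pregnancies result in stillbirth") and ties them to neither algorithm. Nor can the risks be said to be overstated by 18% to 20%, since that holds only at perfect sensitivity.

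The power effect also matters little in practice. Section 9.5 counts 1,021 exposed pregnancies by mid-2022, before eligibility criteria, or about 816 with outcomes (1,021 × 0.80). For SA, power after misclassification would be above 99% at 1:2 and about 96% at five exposed to one comparator. For stillbirth, section 9.5 already concedes that power may be inadequate.

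Finally, section 9.3.1.3 discloses the PPVs and promises to look again for better algorithms, and details may sit in an SAP that is not at hand. Disclosure and a literature check are not a correction, however. The protocol itself grants algorithm cases primary-analysis status, lists its bias analyses and sets the Table 1 condition.

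**Conclusion.** The concern holds in a limited form. SA and stillbirth are analysed from imperfect algorithms on the same footing as confirmed outcomes, and the protocol names no analysis of the resulting error. With sensitivity and false-positive rate equal across cohorts, a true RR of 2.0 appears as 1.82 to 1.83 at any sensitivity. Power at the Table 1 sizes falls from 82% to 83% to about 77% at perfect sensitivity, and to 65% to 68% at 0.80, taking 14% and 1% as true risks. With equal PPV there is no bias in the ratio. The direction of bias in the absolute risks cannot be stated without sensitivity.

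The attenuation matters more than the power, because accrual does not remove it and it bears on how a near-null ratio is read. Both outcomes are secondary and the bias is modest, so this is a worthwhile improvement and not a flaw that undermines the study.

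**What to change.** Add to section 9.7.4 a quantitative bias analysis of the SA and stillbirth risks and prevalence ratios. It should use the cited PPVs, a stated sensitivity range (for example 0.80 to 1.00), and both the common-false-positive-rate and the equal-PPV cases, with results shown beside the uncorrected estimates. The write-up should note that the stillbirth PPV comes from a different type of data source.

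Under Table 1, state that the sizes assume error-free outcome classification, and give the power or the detectable RR under non-differential error.

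The cost is a short calculation on estimates already planned and a slightly less favourable Table 1. No new data or charts are needed.

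### The precision claimed for the 200-livebirth validation sample needs at least 196 adjudicated charts, but the protocol's own access and retrieval rates yield 70 to 85 charts, or 140 to 170 if only record-eligible livebirths are sampled

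*Protocol*

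**What the plan says.** All of the relevant text is in Protocol Section 9.3.1.3.

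- On the sample: "a random sample of 200 livebirths will be selected for medical record confirmation and validation of the livebirth identification algorithm".
- On its precision: "This conservative sample size is sufficient to exclude from the 95% confidence interval (CI) a PPV <80% if the true PPV is 85" per cent.
- On access: "Approximately 50% of patients in the ORD are eligible for medical record retrieval".
- On requests: "For each eligible case, 1 medical record will be requested from 1 provider".
- On success: "approximately 70% to 85% of the medical records are expected to be successfully obtained".
- Combined: "the overall proportion of the ORD available for medical record validation is approximately 35 to 42.5" per cent.

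The section also caps the records to be sought at 550. It does not enlarge the 200 for ineligibility or failed retrieval, provide replacements, or say whether 200 counts livebirths selected, records requested or charts in hand. Section 9.5 ends with a general remark that the final sample size could change, with incomplete record retrieval among the reasons.

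**The concern.** A PPV can be estimated only from charts that are obtained and adjudicated, yet the precision statement is tied to the number of livebirths selected. If the two differ by as much as the section's own rates imply, the interval will be wider than stated.

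What is at stake is how well the livebirth algorithm can be said to perform. This sample is the only validation of that algorithm that the protocol describes. A reader of the protocol would expect values below 80% to be ruled out at the planning PPV of 85%. At the expected yield they would not be.

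**Working it through.** **Inputs (all from Section 9.3.1.3).** Livebirths selected: 200. Planning PPV: 0.85. Value to exclude: below 0.80. Interval: 95%. Eligible for retrieval: 0.50. Requests that succeed: 0.70 to 0.85. Combined: 0.50 × 0.70 = 0.35 to 0.50 × 0.85 = 0.425.

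**Step 1: reproduce the protocol's figure.** For a two-sided normal (Wald) interval whose lower limit is 0.80 at an observed 0.85:

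n = 1.96² × 0.85 × 0.15 / 0.05² = 195.9, so 196.

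At n = 200 the lower limit is 0.85 − 1.96 × √(0.85 × 0.15 / 200) = 0.8005. The figure of 200 reproduces, with a margin of 4 charts. Other common intervals fall just short at n = 200: Wilson 79.4%, exact (Clopper-Pearson) 79.3%. They need about 246 and 254 charts.

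**Step 2: charts expected from 200 selected.**

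- Drawn from all livebirths: 200 × 0.35 = 70 to 200 × 0.425 = 85.
- Drawn only from record-eligible livebirths: 200 × 0.70 = 140 to 200 × 0.85 = 170.

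These are two separate frames. The text does not say which applies.

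**Step 3: lower 95% limit at an observed PPV of 85%.** Normal limit = 0.85 − 1.96 × √(0.1275 / n).

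| Charts | Frame | Normal | Wilson | Exact |
|---|---|---|---|---|
| 70 | all livebirths | 76.6% | 74.8% | 74.5% |
| 85 | all livebirths | 77.4% | 75.9% | 75.6% |
| 140 | eligible only | 79.1% | 78.2% | 78.0% |
| 170 | eligible only | 79.6% | 78.9% | 78.7% |
| 196 | threshold | 80.0% | 79.3% | 79.2% |
| 200 | all charts in hand | 80.05% | 79.4% | 79.3% |

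No expected yield reaches 80% with any of the three intervals.

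**Step 4: what would restore the claim.** To have 200 charts in hand:

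- Eligible only: 200 / 0.85 = 236 to 200 / 0.70 = 286 livebirths.
- All livebirths: 200 / 0.425 = 471 to 200 / 0.35 = 572 livebirths.

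For the minimum of 196 charts the ranges are 231 to 280 and 462 to 560.

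**The case against.** The strongest reply is that nothing was miscalculated. The normal-interval figure reproduces, and 200 could be read as 200 charts that can be validated, with frame and replacement left to the statistical analysis plan. The first half stands: this is not an error in computing 200. The second half does not rescue the text. The protocol itself fixes the number, describes it as livebirths selected, and states the precision, and the same section then gives rates that do not support it. The remark in Section 9.5 is general and does not qualify the claim.

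Other points, and what remains of them:

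- **Size.** With the eligible-only frame the normal shortfall is 0.4 to 0.9 percentage points. That is true, and it is why the point is modest.
- **The 85% is only a planning value.** At an observed 88%, even 70 charts give a normal lower limit of 80.4%. That is also true, but the claim is conditional on 85%.
- **A one-sided 95% limit.** It would reach 80.04% to 80.5% with 140 to 170 charts, but only 78.0% to 78.6% with 70 to 85. A 95% confidence interval is naturally read as two-sided.
- **Stricter intervals and assurance.** Wilson and exact limits are not named in the protocol, and it does not promise a given chance that the lower limit will exceed 80%. These show that the size has little margin, not that 200 was wrongly derived.

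A reader might infer two stronger things. The first is that the denominator of the primary malformation analysis is undermined. The documents do not support that: Section 9.7.2.2 and Table 4 use linked livebirths, and Section 9.4.2 requires an infant record under the same family insurance ID with delivery claims close to the birthdate. A false livebirth with no infant record would not enter. The second is that the validation fails a criterion. The protocol sets no pass/fail rule at 80% and attaches no action to it. Section 9.7.2 also commits to reporting the numbers eligible, retrieved and confirmed, so the actual yield will be visible.

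**Conclusion.** The point holds as a statement of precision that the described sampling does not deliver. It needs at least 196 adjudicated charts. The protocol's own rates imply 70 to 85 (normal lower limit 76.6% to 77.4%) or 140 to 170 (79.1% to 79.6% normal, 78.0% to 78.7% exact), so the conclusion does not depend on which frame was meant. Calling the size conservative is not supported, because the margin is 4 charts with the most favourable of the three two-sided intervals and absent with the other two.

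This rests on a two-sided 95% interval, an observed PPV of 85%, and the stated eligibility and retrieval rates applying to livebirths. If 200 was meant as charts obtained, the normal-interval claim is correct, but the protocol does not say so. The consequence is limited to the precision of the PPV for a secondary outcome. The correction is worth making before records are requested.

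**What to change.** In Section 9.3.1.3, state that the 200 are drawn from record-eligible livebirths, remove the words conservative and sufficient to exclude, and give precision on the charts expected, with one named interval. Suggested text: *Of 200 records requested, 140 to 170 are expected to be obtained; at an observed PPV of 85% the lower 95% limit would be about 79.1% to 79.6% (normal interval)*. If the exact interval is preferred, the figures are 78.0% to 78.7%. This costs wording only and no extra charts; the stated precision becomes slightly less favourable.

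If the sponsor prefers to keep the 80% claim, define the 200 as charts obtained, name the normal interval, and plan for 236 to 286 eligible requests. That is 36 to 86 more than 200 and leaves 264 to 314 of the 550-record cap for malformations and the other adjudicated outcomes listed in Section 9.3.1, so the cap would have to be reconciled with it.
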